**Title: User-Independent Intent Recognition on a Powered Transfemoral Prosthesis**

**NCT #: NCT05537792**

**Document Date: 08/06/2024**

**Protocol and Statistical Analysis Plan**

## 1. **Study Aim, Background and Design**

The primary scientific challenge that this research aims to address is to accurately decode user intent and apply this information to improve control of powered prostheses. The fundamental challenge is to allow users to intuitively control a robotic assistive device by applying wearable sensing technology either in the device or on the user. This is an especially significant research challenge now that advanced mechatronic prosthetic devices have come onto the clinical market and are actively being developed by different research and industry groups. These devices have vast potential to help improve the lives of individuals with a major lower limb amputation, but control systems for such devices need significant improvement [1], [2]. A smart and reliable control interface greatly enhances the user experience in any enterprise and is especially important for controlling complicated mechatronic assistive devices. Users may abandon or under-utilize the technology if the interface between the user and the device—the control system—does not function in an intuitive manner that is safe and convenient for them to use. This proposed research focuses on bridging this important gap.

It is important to further develop prosthetic control technology because of the large impact new technology can have on health outcomes for their potential users. Prosthetic technology is useful to individuals who have suffered from a major lower limb amputation which affects over 650,000 people in the United States [3]. These amputations cause significant disability and decreased quality of life [4]. It results in asymmetric gait that is energetically unfavorable [5] and slower self-selected walking speeds [6] compared to non-amputees. These impairments are due to a variety of reasons such as trauma, disease condition (such as diabetes), congenital limb deficiency, and cancer. There is a critical need for improving the walking capabilities of individuals who have suffered a lower limb amputation to increase their community mobility, independence and ultimately their quality of life.

New and exciting advances have been made on integrating microcomputers, sensors and actuators in mechanical devices to augment lower limb prosthetic technology to solve this need [7], [8]. These devices can help patients reduce their metabolic energy expenditure [9] and traverse more difficult terrain that is often encountered in community ambulation such as slopes, curbs, uneven ground, and stairs. A gap of commercial systems is a lack of sophisticated and robust intent recognition. They instead often rely on the user either using a key fob or performing a set of unintuitive movements unrelated to the movement itself (such as rocking back and forth on the prosthesis) to transition between different modes of operation. Powered prostheses would benefit greatly from an enhanced intent recognition system that seamlessly, automatically, and naturally transitions the device between different modes based on the user's desired activity. Our goal is to develop and evaluate such an intent recognition system that is ready to be deployed in the field on state-of-the-art powered prostheses. These systems can help improve clinically meaningful outcomes in amputee patients including reducing their metabolic cost of walking and increasing their preferred ambulation speed. Additionally, the ability to traverse different terrains more effectively will help improve their community ambulation capability and overall independence as these are commonly encountered outside the home.

One solution that we have previously used to perform intent recognition is to use advanced pattern recognition technology from the machine learning community. Pattern recognition techniques are advantageous because they allow users to be able to seamlessly and automatically shift between modes without having to stop and press buttons on a key fob or perform an unintuitive movement. Instead, we can design a system that recognizes the patterns of sensor information that are generated when humans move and predict a person's movement flow to optimally control both the timing and magnitude of power generation or absorption during movement. One of our previous accomplishments – published in IEEE Transactions on Neural Systems and Rehabilitation – demonstrated that by training pattern recognition systems with transitions between different modes improved the accuracy compared to previous studies from 84.5% to 93.9% [10].

Several leading edge laboratories have studied pattern recognition techniques to improve intent recognition [10]–[13] – including our own previous work – but a significant drawback to these systems are that they are highly user-specific and rely on acquiring large amounts of training data from each subject. Part of this project will focus on developing a user interface that does not need user dependent training data. Voice recognition software previously required users to train the system with their own voice commands and only a relatively small number of people used it. In contrast, state-of-the-art voice recognition software used in cell phones today does not require any user dependent training and is widely adopted. Similarly, intent recognition systems for prostheses must innovate and provide intent recognition systems that require minimal user specific training so that patients will be willing to use them. We propose to do this through novel sensing technology, smarter algorithms, and adapting to each individual user's patterns. We need an innovative approach to achieve an intent recognition system that can be quickly applied to different users without hours of training time or the need for user specific recalibration. A broad goal of this project is to develop signal processing techniques and novel pattern recognition algorithms to enable user-independent intent recognition for powered lower limb prostheses. We will implement a novel adaptation algorithm that will adapt our intention recognition system to new individuals and provide speed-variable prosthetic assistance – eliminating the need to for any user dependent training. These algorithms will be implemented on the Open Source Leg (OSL) powered prosthesis, which was designed by collaborator [name] [14]. A minimum group of ten individuals who use a prosthetic knee and foot in their clinically prescribed prosthesis will be trained on the powered leg and will complete the experiment. We will compare the accuracy of the intent recognition systems in walking speed estimation and also measure other clinically meaningful parameters including self-selected walking speed and relevant biomechanics. We expect adapted systems to exhibit advantages in walking speed estimation error compared to non-adapted systems and provide appropriate powered response for each walking speed during treadmill and overground walking.

## **2. Participant population**

Subjects must fit into one of two categories stated in the study design section: able bodied individuals, and disabled individuals/amputees. Disabled individuals are considered

part of a vulnerable population. This group will be protected through the use of safety equipment such as hand rails and a safety harness for the case of stumbles and falls. The goal is to collect data from at least 10-15 participants from the amputee population.

Participants will be between 18-75 years old. Inclusion criteria includes subjects must be between 18-75 years of age, use a prosthetic knee and foot in their clinically prescribed prosthesis (except for the able bodied subjects). Subjects must be at K3 or K4 ambulatory level according to the Medicare/Medicaid designation as the study requires subjects to walk, ascend/descent stairs and ascend/descend ramps. Subjects will be excluded if they have any history of a neurological injury, gait pathology, or a cardiovascular condition that would limit their ability to ambulate for multiple hours during the experimental sessions. Pregnant subjects will also be excluded to the risk of a fall during the experiment.

All participants that meet the appropriate criteria will be recruited through official flyers and verbal scripts, even if they are already known to the researchers. Flyers will be posted around the campus of Georgia Institute of Technology, in designated advertising areas. Additionally, word of mouth recruiting will use a script with similar language as the flyers. Recruiting materials are attached as separate documents including a flyer and e-mail script. Permission will be obtained from participants before using any information for research purposes that has individual identifiers attached.

### **3. Study Procedures**

This will be a single-visit study. If participants are not able to complete the study during their first visit, they will be asked to return. All testing will take place at the Georgia Tech Manufacturing Institute (GTMI) at the Georgia Institute of Technology. Testing will last between 2-3 hours with no more than 30 minutes of continuous movement and visits will be scheduled at the convenience of the participants.

Able bodied individuals may be fitted with a commercialized assistive walking device, iWALK (user manual attached as separate document), that has been adapted in order to be used with the prosthetic device. This is to ensure controllers are functioning before a subject comes in and walks on the prosthetic device. During all testing participants are instructed to vocalize any concerns or discomfort to researchers. At any time if participants are uncomfortable, they have the right to quit the study with no penalty. The first visit will last no longer than 4 hours. If the participant obliges, they will be asked to return for additional visits, scheduled at their convenience. During additional visits, human participants will be asked to perform typical tasks such as standing, sitting, or walking, in a safe and monitored environment. Tests will begin on a treadmill with a security harness and or gait belt, based on the level of comfort of the participant. If the participant feels comfortable, testing will be moved from the treadmill to the floor for supported and then freestanding walking. Another type of treadmill is a force-instrumented treadmill incorporated into the Computer Assisted Rehabilitation Environment (CAREN). This treadmill is embedded in a large platform that is able to move in six degrees of freedom, allowing the application of disturbances during standing or walking by moving the platform. During all types of testing in which subjects are asked to respond to environmental disturbances, they will be required to wear a safety harness. During tests, verbal feedback

from the participants will be used to improve the comfort of the devices. Participants are instructed to notify researchers if they feel unsafe, and may quit the study at any time without penalty. Testing will first be conducted on able-bodied individuals until the PI feels that it is safe to transition to disabled individuals/amputees. Testing with disabled individuals will only occur after initial tests can be run without functional errors involving either hardware or software. Once the software and control system of the devices are thoroughly tested on able bodied users the optimized device be used for testing with disabled individuals. Additionally, participants may be asked to wear EMG sensors, markers for measuring biomechanics, other mechanical sensors (such as IMUs) and a metabolic mask. One of the metabolic masks and heart rate monitor comprise an FDA approved metabolic system called the COSMED Fitmate Pro. Another type of a metabolic measurement system may be used such as the ParvoMedics TrueOne 2400 metabolic cart. The Fitmate Pro or ParvoMedics system will be demonstrated to the participant, after which they will choose whether or not they are willing to use this system. All participants will be guided through the following general procedure during their visits, requiring action on their part:

- Participants will be briefed about the details of and their rights during the study.
- The prosthetic and attachment interface will be fit to the participant, along with any additional data collection equipment.
- Participants will be guided through the specific activities of the study, detailed already.
- Participants will receive assistance removing any hardware used during the study.

Other equipment may be utilized to measure biomechanics of the user during ambulation. Specifically, we will be using a VICON motion capture analysis system. This will also us to measure biomechanical similarities and differences while using the powered prosthesis compared to the sound side limb. Also, some protocols will require the use of an EMG (electromyography) system to measure muscle activity across different ambulation tasks. Three systems may be used which includes the Delsys Trigno Wireless EMG system, Biometrics Ltd. EMG system, and COAPT EMG system. All of these systems will use electromyography sensors that will be placed on the surface of the user's skin.

In order to also measure functional clinical measures, a Protokinetics gait mat will be utilized to measure common measures such as step length, step time, and symmetry. This system is just a mat that users will need to walk on top similar to walking overground. Users will be in a harness and have the options for handrails or gait belt if needed.

Throughout the tests there will be a camera recording the session. The purpose of the camera is to record performance for future analysis. The participant will always have the right to stop the test and/or take a break. The participant may also choose to discontinue participation at any time.

This study will ask participants to walk on treadmill and overground settings to adapt pre-trained (baseline) walking speed estimation machine learning (ML) models to user-specific data. The adaptation pipeline self-labels and updates models with user data in real-time. We explore two methods of self-labeling referred to as Direct Integration (DI) and Ground Truth (GT). DI computes walking speed labels using heel-to-heel foot

displacements measured by a foot inertial measurement unit (IMU). GT provides labels that are the true treadmill speed (for treadmill trials) or center-of-mass speed (for overground trials). Treadmill speed profiles follow either a staircase profile (P1) or a triangular profile (P2). Overground walking is constrained to a 5-meter straight path between two cones. Adapted models are renamed based on the environment (P1, P2, or OVG) and labeling method (DI or GT) used. Models are evaluated on how well they can estimate the current speed (forward estimation). Additionally, we provide biomimetic assistance that scales with estimated walking speed.

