#### **5. Research Risks**

The main risk of the study is a possible fall. Each participant will be given ample time to get accustomed to using the devices. This adjustment period will involve getting used to balancing with the given device or control method. In this adjustment period, participants run the highest risk of falling. However, to manage this risk, there will be rails around the treadmill at all times, which the user may hold to prevent falls. Based on the participant's comfort, there are varying levels of additional treadmill support or padding. After the adjustment period, if the participant is comfortable enough for freestanding walking there will be spotters next to them at all times. When testing the prosthetic, there is an additional risk of irritation caused by the method of attachment. The level of risk varies depending on the walking style and skin sensitivity of the participant. To reduce the likelihood of irritation, amputees will use their own prosthetic socket and non-amputees will use a commercial assistive walking device. The instruction manual for the commercialized assistive walking device (iWALK) is attached as a separate document.

Participants are strongly encouraged to vocalize any discomfort to try and prevent irritation from occurring. If irritation does occur, brief medical care in the form of disinfectant wipes and/or a Band-Aid will be provided. In the unlikely event of an irritation too severe for a Band-Aid, the participant will be referred to a physician. Any adverse events will be reported to ORIA within the regulated time frame. If the metabolic system is used by the participant, there are slight risks associated with the system. They include transmission of communicable diseases, aspiration of contaminants, irritation from wear, choking/strangulation, and discomfort. To protect against infection, the mask and monitor will be properly disinfected between uses, and will always be handled with disposable

sanitary gloves. Also, antibacterial filters will always be used with the metabolic mask to prevent aspiration of contaminants.

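### For the adjustment period, which the protocol ranks highest for falls, no harness is required, and an amputee may start treadmill tests on a gait belt alone

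*Combined protocol and SAP*

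**What the plan says.** Section 2 (Participant population) treats disabled participants as vulnerable and says that they "will be protected through the use of safety equipment such as hand rails and a safety harness for the case of stumbles and falls". It ties this to no stage or task.

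Section 3 (Study Procedures) sets the rule for treadmill work: "Tests will begin on a treadmill with a security harness and or gait belt, based on the level of comfort of the participant". It then describes the move to the floor: "If the participant feels comfortable, testing will be moved from the treadmill to the floor for supported and then freestanding walking". The same section requires a safety harness whenever participants respond to environmental disturbances. It also says that users of the gait mat are in a harness, with handrails or a gait belt as options.

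Section 5 (Research Risks) identifies a fall as the main risk and describes a period in which participants get used to the device: "In this adjustment period, participants run the highest risk of falling". To manage that risk, "there will be rails around the treadmill at all times, which the user may hold to prevent falls", and, depending on the participant's "comfort, there are varying levels of additional treadmill support or padding". Spotters come later: "After the adjustment period, if the participant is comfortable enough for freestanding walking there will be spotters next to them at all times".

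**The concern.** The protocol ranks its own stages by fall risk, yet for the riskiest one it writes down no fixed harness rule. Rails are always present, but holding them is optional. Any further support depends on how comfortable the participant feels, and no minimum is set. Someone new to a powered knee and ankle may feel comfortable before being stable, so comfort is a weak basis for deciding whether to wear a harness.

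The practical consequence is inconsistency. Two members of staff, both complying with the protocol, could start the same amputee in a harness or on a gait belt alone. What is at stake is participant safety. The speed-estimation error and its analysis in Section 4 do not depend on this.

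**Working it through.** No arithmetic applies. The check sets every statement on harness, gait belt, rails and spotters side by side.

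1. **Where the risk is highest.** Section 5 says that it is the adjustment period.

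2. **What Section 5 states for that period.** Rails, to be held at the user's choice, and support or padding by comfort. The support may be meant to include the harness, but comfort still decides. Spotters are stated only for freestanding walking afterwards.

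3. **Whether the Section 3 treadmill sentence covers that period.** This is an inference. Both sections put a treadmill stage before freestanding walking, which favours the link. Against it, the sentence does not mention the adjustment period, it applies to able-bodied participants as well, and it follows one about later visits: "During additional visits, human participants will be asked to perform typical tasks such as standing, sitting, or walking, in a safe and monitored environment". The two readings are:
   - If the sentence applies, comfort decides between harness, gait belt or both, and a gait belt alone complies.
   - If it does not apply, only the measures in step 2 are stated.

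   On either reading, no harness is required and no spotter is stated for the adjustment period. Whichever reading is right, a gait belt alone also complies when treadmill tests begin.

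4. **How other activities are handled.**
   - Disturbance tests (Section 3): harness required.
   - Gait mat (Section 3): users in a harness, gait belt optional. The protocol likens this task to overground walking.
   - Freestanding walking (Section 5): spotters throughout.

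   For the gait mat, the harness is the base and the gait belt the extra. At the start of treadmill testing, the gait belt may stand in for the harness.

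5. **What else lowers the risk.** Able-bodied testing comes first, and amputees are tested only once initial tests run without functional errors (Section 3). Entry is limited to K3 or K4 ambulators (Section 2). Participants get ample time to adjust (Section 5), the environment is monitored, and they may stop at any time (Section 3). These make a fall less likely. They do not settle what protects a participant who stumbles.

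6. **Who is affected.** Every amputee participant: a minimum of ten trained on the powered leg (Section 1), with a goal of at least 10-15 (Section 2).

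**The case against.** The strongest reply is that the protocol describes complementary protection: rails where the treadmill provides them, a harness or gait belt from the start of treadmill tests, and spotters once the person walks freely. On this view the adjustment period is well covered, and a firmer sentence would only tidy the wording. Section 12 adds that testing of this device was previously approved by the ethics board under a similar protocol, and that the principal investigator has run similar experiments with amputees. Much of this stands. It lowers the urgency, and nobody should read the adjustment period as unprotected. It does not remove the option of starting an amputee on a gait belt alone.

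A reader might infer that Section 3 breaks a commitment made in Section 2. The documents do not support that. Section 2 lists examples and fixes no stage, so rails plus a comfort-based choice are compatible with it.

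A reader might also infer that no harness is mandated anywhere in the study. That is wrong: the disturbance-test and gait-mat rules say otherwise. The gap is confined to the adjustment period and the start of treadmill testing.

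Finally, it can be objected that a harness for all amputee treadmill walking goes further than the adjustment period. That is true, and the documents do not say that the later speed profiles or the speed-scaled assistance raise fall risk. But the protocol neither says when adjustment ends nor links the Section 3 sentence to it. A rule covering both avoids leaving that boundary to judgement on the day.

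**Conclusion.** The point holds as a limited safety improvement. The protocol names its period of highest fall risk and leaves harness use in it to comfort, or unstated, while requiring or stating a harness for two other activities. Following the text, an amputee can begin treadmill tests on the powered leg with a gait belt alone.

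Its reach is every amputee participant. Its size in falls or injuries cannot be given, because the documents contain no event rate, and none is needed to justify so small a change. The conclusion about the adjustment period does not depend on treating the Section 3 sentence as describing it.

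Two limits apply. Nothing here shows that participants were or will be harmed. Nothing here affects the error estimates, the repeated measures ANOVA or the paired t-tests. It is a change worth making because it is cheap, and not a defect that puts the study's results in doubt.

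**What to change.** In Section 3, replace the sentence on how treadmill tests begin with wording such as: *Treadmill testing comes first. Amputee participants wear the safety harness throughout the adjustment period and whenever they walk on the treadmill with the powered prosthesis; a gait belt may be added but does not replace the harness. Able-bodied participants use a harness, a gait belt or both, according to comfort.*

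In Section 5, after the sentence on rails, repeat the rule: *Amputee participants wear the safety harness during the adjustment period.*

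Optionally, extend the existing spotters back to the adjustment period, provided that this needs no extra staff. The documents do not give staffing for that period, so the sponsor would have to confirm it. The rules for disturbance tests, the gait mat, comfort-based padding and freestanding walking stay as they are.

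The cost is one amendment that replaces one sentence and adds another. The protocol already names the harness, so no new type of equipment is introduced. The downside is that amputee participants lose the gait-belt-only option on the treadmill.
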